Effect of Caffeinated Chewing Gum on Dehydration ability in

Bodybuilding Athletes: a crossover trial

Document Date: May 23, 2024

Project summary

The purpose of this study was to investigate the effect of caffeinated chewing gum on

dehydration ability in bodybuilding athletes. Methods: 15-20 trained bodybuilding

athletes were divided into caffeine gum trial (CAF) and placebo trial (PL) with a

randomized, double-blind study design. The participants chewing either caffeine Gum

(CAF trial, containing 5 mg/kg of caffeine) or placebo gum (PL) for 10 minutes. After

rested for 15 minutes, Participants used the bicycle to adjust the pedal resistance and

speed according to their own feelings until they were dehydrated to 2% of their original

body weight. Record time from exercise to completion of dehydration, heart rate, HRV,

energy expenditure, fat oxidation rate and carbohydrate oxidation rate.

Introduction

Many athletes use caffeine (1, 3, 7-trimethylxanthine) as a nutritional supplement,

which is widely available in everyday foods such as coffee, chocolate, tea, cola and

energy drinks. Caffeine intake can reduce fatigue by inhibiting adenosine receptors,

increase the ability of the sarcoplasmic reticulum to release calcium ions, maintain

sodium-potassium ATPase activity, and increase glycolysis before exercise(1, 2), all of

which are mechanisms that can significantly increase sprinting speed (3), repetitive

sprinting ability, and maximal muscular strength and explosive power (4). These

increases in physical performance may be effective in improving athletic performance.

Previous studies have shown that a pre-exercise caffeine intake of 3-6 mg per kilogram

of body weight can achieve the highest concentration in the bloodstream one hour after

intake (5, 6), resulting in performance enhancement. However, caffeine is slowly absorbed in the gastrointestinal tract and may cause gastrointestinal discomfort or excessive fluid intake (8). Finding alternative forms of caffeine supplementation may reduce gastrointestinal discomfort.

Caffeine supplementation using caffeinated gum before exercise has been found to be absorbed through the oral mucosa at a faster rate than caffeine capsules (7). In a study by Morris et al. in 2019, test subjects chewed gum containing 100 mg of caffeine for 2, 5, and 10 minutes to observe their caffeine absorption rate and blood levels. The results showed that 85% of the caffeine was effectively absorbed after 5 minutes of chewing caffeinated gum, and after 10 minutes, the caffeine in the gum was almost completely absorbed. In terms of blood concentration, the highest concentration of caffeine (8) was observed after 15 minutes of chewing caffeine gum. In terms of exercise performance, chewing gum containing 100-300 mg of caffeine 5-15 minutes before exercise can effectively improve aerobic capacity, slow down the decline of sprinting speed, increase vertical jump height, and enhance the effect of explosive power (9, 10).

Caffeine supplementation has been shown to be effective in enhancing aerobic exercise performance; however, it remains unclear whether chewing caffeine has the same significant effect on dehydration ability in bodybuilding athletes. Therefore, the purpose of this study was to investigate the effect of caffeine chewing gum on dehydration ability by aerobic exercise.

Methods

Design

This study used a randomization crossover design with double-blind experimental design. Participants will be divided into a caffeinated chewing gum trial (CAF) and a placebo trail (PL). The placebo trail (PL). After the first trial, the participants rested and recovered for 7-10 days before the next trial, which was expected to be completed within one month. During the trial period, all participants maintained their normal training status, with no changes in training or retraining menus, and no over-training or extra competitions.

Participants

In this study, 15-25 trained bodybuilders were recruited. All participants had more than 6 years of professional bodybuilding training and had participated in national bodybuilding competitions with adequate pre-competition dehydration experience. Inclusion criteria were: 1. having won the top 8 places in a national competition, 2. having no cardiovascular or joint diseases, and 3. being an adult male. Exclusion criteria were: 1. no top 8 finishes at national level; 2. cardiovascular or joint disease, or any other condition that could be impaired by exercise; 3. female and underage participants; 4. previous caffeine allergy. This study received approval from the Institutional Review Board of Jen-Ai Hospital - Dali Branch (202300071B0). This study was conducted following the Declaration of Helsinki.

Protocol

Pre test

Prior to the main experiment, all participants underwent a 15-minute sub-maximal exercise intensity test to understand the relationship between exercise intensity and heart rate, energy expenditure, fat expenditure, and carbohydrate consumption. The

methodology of this study has been used in the literature in the past(11). After wearing a heart rate monitor (RS800; Polar Electro Oy, Kempele, Finland), participants rested for 10 minutes in a standing position and heart rate values were obtained while standing. Next, participants were placed on a gas analyzer (Vmax Series 29C, Sensor Medics, CA, USA) and tested at different speeds of 1, 2, 3, 4, and 5 miles per hour on a 0-degree incline for 3 minutes each. Heart rate and energy expenditure during exercise were recorded for subsequent studies.

Experimental procedure

All experiments were scheduled to begin at 9:00 am. Upon arrival at the laboratory, participants will first have their urine (specific gravity) measured using a hydrometer (AAnalyst 800, Perkin Elmer, Waltham, MA) to record whether they are sufficiently hydrated (specific gravity < 1.020). Participants with a specific gravity > 1.020 were provided with 500 mL of bottled water to drink for 15 minutes prior to the start of the test until adequate hydration was achieved. Such an experimental procedure for dehydration has been used in previous studies (12).

When participants reached the same hydration state, they were fitted with a heart rate monitor (RS800; Polar Electro Oy, Kempele, Finland) and chewed either caffeine gum (5 mg/kg for 5 minutes per chew) or a placebo (5 minutes per chew, using regular gum). Take a 15-minute break after chewing and perform a brief warm-up and stretching. It was expected that the exercise environment would be set at 30°C and 50% humidity using air conditioning. After the warm-up, participants were free to adjust the resistance and speed of the bike according to their own feelings by riding the bike, and they were free to arrange the rest time. After 30 minutes of riding, the weight of the participant was measured every 10 minutes until dehydrated to 2% of their original body weight. The time from exercise to dehydration was recorded, and energy

expenditure, fat oxidation rate, and carbohydrate oxidation rate were calculated from the regression curve. At the end of the exercise, urine samples were collected again to analyze the data.

Caffeine and placebo gum

The caffeinated chewing gum (Military Energy Gum, Arctic Mint flavor; Stay Alert, Chicago, USA) and placebo used in this study were the same as previous study (13). All gums were crushed, ground, blended and reshaped, and flavored with 0.3 g of peppermint flavoring powder to ensure that their appearance, color, taste, weight and size were similar to the original gum. After chewing the gum, the participants completed a questionnaire to verify whether they could distinguish between the two types of gum.

Statistical analysis

The data in this study are presented as mean \pm standard deviation. The Shapiro–Wilk test was used to examine the normality of the data. When normality distribution was reached, energy expenditure, dehydration rate, and urine specific gravity between the two groups were analyzed using the paired-sample t-test. If the normative distribution was not reached, it was analyzed using the Wilcoxon sign rank. Significant levels were set at $\alpha < 0.05$.

Reference

- 1. Kalmar JM. The influence of caffeine on voluntary muscle activation. Medicine and science in sports and exercise. 2005;37(12):2113-9.

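### Ride energy expenditure and fat and carbohydrate oxidation are read from a curve built in level walking or running, not cycling, and the protocol does not ensure that heat or heart-rate range match the ride

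*Protocol*

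**What the plan says.** Protocol, Methods, Pre test: each athlete completes a "15-minute sub-maximal exercise intensity test" before the main experiment, intended to link exercise intensity with heart rate, energy expenditure, and fat and carbohydrate use. Heart rate at rest is taken standing. With a gas analyser, athletes are then "tested at different speeds of 1, 2, 3, 4, and 5 miles per hour on a 0-degree incline for 3 minutes each". The section ends: "Heart rate and energy expenditure during exercise were recorded for subsequent studies".

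Protocol, Experimental procedure: in the main sessions "participants were free to adjust the resistance and speed of the bike according to their own feelings by riding the bike", with rest also at their discretion. The "exercise environment would be set at 30°C and 50% humidity using air conditioning". The ride continues until 2% of body weight is lost. Energy expenditure, "fat oxidation rate, and carbohydrate oxidation rate were calculated from the regression curve".

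Protocol, Statistical analysis: energy expenditure is one of three variables compared between the trials by a paired test; the others are dehydration rate and urine specific gravity. The Project summary lists energy expenditure and both oxidation rates among the recorded outcomes.

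**The concern.** A calibration curve is valid for the conditions in which it was built. Here it is built on foot and applied to cycling. Speed on foot cannot be converted to a self-chosen pedal resistance, so something else must carry the curve from one session to the other. The Protocol does not name the regression's predictor. Heart rate is the only candidate described in both sessions, since the same monitor is worn in each. The calculation then assumes that a given heart rate means the same metabolic rate and fuel mix in upright walking or running as in seated cycling. Nothing in the document supports that assumption, and posture and active muscle mass give reason to doubt it.

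Two further conditions are left open. The 30°C and 50% humidity are stated only for the ride, and nothing requires the 5 mph top stage to reach the heart rates of the ride.

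At stake are the validity of one formally tested outcome, energy expenditure, and of two listed outcomes, the oxidation rates.

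**Working it through.** **1. Is there room for a cycling stage in the pre-test?** Stages × minutes = 5 × 3 = 15 minutes. This reproduces the stated length, so the stages on foot are the whole test.

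**2. The two sessions side by side**

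| | Pre test | Ride |
|---|---|---|
| Mode | 1–5 mph, no incline; rest standing | Bicycle |
| Intensity | Fixed stages | Chosen by the athlete; no range given |
| Environment | Not stated | 30°C, 50% humidity |
| Gas analysis | Yes | None described |
| Heart rate monitor | Yes | Yes |

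Only the difference in mode is shown by the text. The word treadmill does not appear, but speed in miles per hour on an incline, with standing rest, is not cycling. Heat and range are unspecified.

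**3. Which errors survive the crossover?** Suppose the correct cycling relation is rate = a + b × HR, and the curve used has intercept a + d and slope b + e. Let T be ride time.

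- Difference of rates: (b + e) × (HR_CAF − HR_PL). The constant d cancels. The slope error scales the difference by (b + e)/b.
- Difference of totals: the constant leaves d × (T_CAF − T_PL), which is zero only if ride times are equal.
- Level in either trial: both d and e remain.

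**4. Illustrations. All inputs here are assumptions, not in the document.**

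- *Constant error, totals.* A heart rate 10 beats/min away from the curve at the same metabolic rate, with slope 0.10 kcal/min per beat, gives d = 10 × 0.10 = 1 kcal/min. With ride times 10 minutes apart, 1 × 10 = 10 kcal of false difference remains. In a difference of rates, 1 − 1 = 0 remains.
- *Proportional error.* With a true rate of 8 kcal/min and rides of 80 and 90 minutes, the true difference in totals is 8 × (80 − 90) = −80 kcal. A curve 20% too low gives 0.8 × (−80) = −64 kcal; 20% too high gives 1.2 × (−80) = −96 kcal. The sign is kept and the size is wrong.
- *Range.* For a straight line through five equally spaced stages, the standard error of the fitted value, relative to the residual SD, is √(1/5 + (x − 3)²/10), where x is the position in stage-widths.

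| Position x | Relative standard error |
|---|---|
| 3 (middle stage) | √0.20 = 0.45 |
| 5 (top stage) | √0.60 = 0.77 |
| 6 | √1.10 = 1.05 |
| 7 | √1.80 = 1.34 |
| 8 | √2.70 = 1.64 |

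If the ride lay one to three stage-widths above the top stage, precision would worsen by these amounts even with a correct straight line. Whether it does lie there cannot be told from the Protocol.

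**The case against.** The strongest defence is the design. Each athlete is his own control and one curve serves both trials, so an error constant within the athlete drops out of a paired difference of rates. A proportional error rescales a true difference but does not create one. The stated aim is dehydration ability, and time to 2% loss, body weight and urine specific gravity are measured without the curve. The oxidation rates are not named among the tested variables. The pre-test also follows a cited earlier method.

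Most of this stands, and it limits the reach of the point. It does not protect reported levels, totals over unequal ride times, or the size of a difference. The Protocol does not say whether energy expenditure is analysed as a rate or a total. Earlier use of a method does not show that it is valid for cycling.

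Two stronger readings are tempting, and the document supports neither. A reader might infer that the curve also comes from the wrong temperature and too low an intensity. But the pre-test temperature and the ride intensity are not given, so these are gaps in specification. A reader might also infer that upward drift of heart rate, growing with ride time, puts a false difference between the trials. But both rides stop at the same 2% loss. Drift that follows fluid loss, if it builds linearly, has the same end point and the same average in both trials, and so cancels in a difference of rates. Only a component driven by time itself, or the use of totals, would leave something, and the document has no figures from which to size it.

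**Conclusion.** The point holds for exercise mode: the curve comes from level walking or running and is applied to a bicycle ride, and the derived energy expenditure is then tested. For heat and heart-rate range, the Protocol fails to ensure a match; it does not show a mismatch.

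Reported levels of the three measures, totals over unequal ride times, and the size of any caffeine–placebo difference through slope error may be biased. The document gives no basis for estimating the actual error. The 10 kcal and 64–96 kcal figures only show how such errors act under assumed values, with heart rate taken as the predictor. Outcomes measured directly in the ride session are unaffected. The change is worth making because it improves a tested outcome cheaply, but the dehydration conclusions do not depend on it.

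**What to change.** Run the same 15-minute, five-stage pre-test, with the same gas analyser and heart rate monitor, on the bicycle used for the ride. Take resting heart rate seated on it. Set the stages by resistance so that they span the heart rates expected in the ride, and hold the test at 30°C and 50% humidity where the equipment allows. State the regression's predictor, and whether energy expenditure is compared as a rate or a total.

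Report how much ride time falls outside the calibrated heart-rate range and label those values as extrapolated. Do not delete them: heart rate in the ride is observed after the gum is chewed, so dropping data by heart rate could remove different amounts from the two trials.

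The cost is a short amendment to the Pre test section, with the same test length and instruments, plus use of the heated room if the analyser can work there. The pre-test would no longer match the cited earlier method exactly. A short test without fluid loss also cannot capture heart-rate drift from dehydration, so that limitation remains and should be stated.

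### A one-sided hydration limit is called the same hydration state, and the plan does not say which urine specific gravity reading is tested or how the pre-gum reading is used

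*Protocol*

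**What the plan says.** Protocol, Methods, Experimental procedure: on arrival, urine is tested to "record whether they are sufficiently hydrated (specific gravity < 1.020"). For readings above the limit, "Participants with a specific gravity > 1.020 were provided with 500 mL of bottled water" until hydration is adequate. No lower limit is set, and no tolerance between one man's two visits. A reading of exactly 1.020 falls under neither rule. The next step opens "When participants reached the same hydration state, they were fitted with a heart rate monitor". After the ride, "At the end of the exercise, urine samples were collected again to analyze the data".

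Protocol, Statistical analysis: "energy expenditure, dehydration rate, and urine specific gravity between the two groups were analyzed using the paired-sample t-test". The fallback is "If the normative distribution was not reached, it was analyzed using the Wilcoxon sign rank". Neither sentence says whether the specific gravity tested is the post-ride value, the change from arrival, or each time point in turn. No covariate is named.

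**The concern.** Passing an upper limit puts two visits in the same category; it does not make them equal. The protocol nevertheless describes the visits as equal at the start and names an analysis with no baseline term. Post-ride specific gravity probably depends in part on how concentrated the urine was at the start. If so, an unadjusted comparison of post-ride values carries the start difference between the CAF and PL visits in every paired difference.

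What is at stake is precision in a trial of 15 to 25 men (15 to 20 in the Project summary). Urine specific gravity is one of three outcomes named for testing. The within-visit baseline that could remove the noise is already measured, but its role is left open, and the possible analyses (post-ride value, change score, adjusted value) do not perform alike.

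**Working it through.** The plan gives no standard deviation, effect size, correlation or power for this outcome, so there is no stated figure to reproduce. From the documents: the limit of 1.020, n of 15 to 25, a randomised crossover, significance level 0.05 (taken as two-sided). Everything else below is an assumption.

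**1. What the limit allows.** Start values of 1.004 and 1.019 both pass. The start difference is 0.015.

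**2. Noise added to an unadjusted post-ride comparison.** Assume start values spread evenly over 1.002 to 1.019, so SD = 0.017/√12 = 0.00491. With between-visit correlation ρ, the SD of the start difference is 0.00491 × √(2(1 − ρ)): 0.00694 at ρ = 0 and 0.00491 at ρ = 0.5. If a share c carries into the post-ride value and the remaining paired SD is 0.004, the variance of the paired difference is multiplied by 1 + (c × SD of start difference)²/0.004².

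| c | ρ = 0 | ρ = 0.5 |
|---|---|---|
| 0.3 | 1.27 | 1.14 |
| 0.5 | 1.75 | 1.38 |
| 0.8 | 2.93 | 1.96 |

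With a remaining SD of 0.006, c = 0.3 and ρ = 0.5, the factor falls to 1.06.

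**3. Power of the three analyses.** Let pre and post values have equal between-visit SD s and within-person correlation r. The variance of the paired difference is then 2s² for the post-ride value, 4s²(1 − r) for the change score and 2s²(1 − r²) for the adjusted value. With a standardised effect of 0.6 on the post-ride value, the effect becomes 0.6/√(2(1 − r)) for change and 0.6/√(1 − r²) for the adjusted value. Power is from the noncentral t with n − 1 degrees of freedom (n − 2 when adjusted). Example: n = 15, r = 0.5 gives 0.6/√0.75 = 0.693, noncentrality 0.693 × √15 = 2.68, power 0.699.

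The adjusted formula treats the mean baseline difference as exactly zero. In a real sample it is not, and estimating the slope multiplies the variance by about (n − 2)/(n − 3) on average for normal data: 13/12 = 1.083 at n = 15 and 23/22 = 1.045 at n = 25. The last column is the power of the fitted regression intercept, from 200,000 simulated normal trials per row.

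| n | r | post-ride only | change | adjusted, formula | adjusted, simulated |
|---|---|---|---|---|---|
| 15 | 0 | 0.580 | 0.334 | 0.576 | 0.546 |
| 15 | 0.3 | 0.580 | 0.448 | 0.616 | 0.587 |
| 15 | 0.5 | 0.580 | 0.580 | 0.699 | 0.668 |
| 15 | 0.7 | 0.580 | 0.797 | 0.852 | 0.824 |
| 20 | 0 | 0.721 | 0.437 | 0.718 | 0.695 |
| 20 | 0.3 | 0.721 | 0.576 | 0.758 | 0.734 |
| 20 | 0.5 | 0.721 | 0.721 | 0.834 | 0.813 |
| 20 | 0.7 | 0.721 | 0.907 | 0.944 | 0.931 |
| 25 | 0 | 0.821 | 0.530 | 0.819 | 0.802 |
| 25 | 0.3 | 0.821 | 0.682 | 0.853 | 0.837 |
| 25 | 0.5 | 0.821 | 0.821 | 0.912 | 0.900 |
| 25 | 0.7 | 0.821 | 0.960 | 0.980 | 0.976 |

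By formula the gain over post-ride only is nil at r = 0, 3 to 4 points at r = 0.3 and 9 to 12 at r = 0.5. By simulation it is a loss of 2 to 4 points at r = 0, a gain of about 1 to 2 at r = 0.3 and 8 to 9 at r = 0.5. Setting (1 − r²)(n − 2)/(n − 3) = 1 gives r² = 1/(n − 2), so adjustment breaks even near r = 0.28 at n = 15 and r = 0.21 at n = 25. The change score is worse than post-ride only whenever r is below 0.5.

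**4. Validity.** With no gum effect, start values uniform on 1.002 to 1.020, half of each carried through and residual SD 0.004 per visit, the post-ride paired t-test rejected in 0.051, 0.051 and 0.050 of 40,000 simulated trials at n = 15, 20 and 25.

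**The case against.** The strongest reply is that the text never says the arrival value is left out. A paired t-test could be run on the change, and the choice of variable and covariate is commonly settled in a statistical analysis plan, which may exist. This stands: a reader might infer that the plan ignores the pre-ride reading, but that turns silence into a decision. What the reply does not reach is the protocol's own description of the visits as equal, which its own rule does not deliver, and the fact that both tests it names lack a baseline term.

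A reader might also infer that a chance imbalance in start values would pass for a gum effect. The documents do not support this. Visit order is randomised, the arrival reading precedes the gum, and start differences already sit inside the paired SD, so the false-positive rate stays at its nominal level.

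The gain may also be negligible. This stands at low r, and the larger variance factors in step 2 rest on independent visits and high carry-through. All rides start at 9:00 am with training unchanged, so some between-visit correlation is plausible.

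Finally, the wording may mean only that everyone was adequately hydrated. That is a fair charitable reading, and one more reason to say it.

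**Conclusion.** The point holds as one of description and precision. The limit of 1.020 is one-sided, so the visits need not start equal, and the protocol leaves open which specific gravity reading is tested. If it is the unadjusted post-ride value, the cost is lost precision, with no bias and no excess of false positives. The size runs from nothing to about 9 to 12 points of power at r = 0.5 by formula, or 8 to 9 once slope estimation is counted, for n = 15 to 25 and an assumed effect of 0.6. It would be larger if r is higher. The effect size, r, start-value spread and carry-through are all assumptions.

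It would be tempting to extend this to dehydration rate. The documents give no basis for a carry-over of starting specific gravity into that outcome, and nothing was computed for it, so the point is confined to urine specific gravity, which is not designated primary.

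**What to change.** - In Experimental procedure, replace the statement that participants were in an equal state with one that the hydration threshold was met. State that specific gravity is re-measured after any water, and that the last pre-gum reading is that visit's baseline.
- The sponsor should reconcile the two rules around 1.020, which leave a reading of exactly 1.020 unassigned.
- In Statistical analysis, name post-ride specific gravity as the tested variable. Regress the within-person CAF minus PL difference on the CAF minus PL baseline difference, with zero difference as the reference point, so that the intercept is the gum effect. A model with participant effects, treatment and visit baseline is equivalent if participants are fixed, or if each man's mean baseline is also included when they are random. Do not use a simple change score.
- If residuals are clearly non-normal, use a permutation test that swaps the CAF and PL labels within a participant for both differences together, or a rank-based version. The Wilcoxon test as named takes no covariate.

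The cost is one degree of freedom, a small penalty for estimating the slope (2 to 4 points of power if r is really zero), and a replaced test for this one outcome. The procedure already measures specific gravity before the gum and collects urine after the ride; the reading after water only needs to be recorded.

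### The two-visit crossover is tested with a paired t-test or signed-rank test that leaves out the visit effect, which costs precision and, if the two orders are unequal, shifts the estimate

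*Protocol*

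**What the plan says.** The Design section of the protocol states: "This study used a randomization crossover design with double-blind experimental design". Each athlete attends twice: "After the first trial, the participants rested and recovered for 7-10 days before the next trial". The section does not say how order is allocated, or that the two orders will be equal in size.

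The Statistical analysis section fixes the comparison: "energy expenditure, dehydration rate, and urine specific gravity between the two groups were analyzed using the paired-sample t-test". If the Shapiro–Wilk test rejects normality, a Wilcoxon signed-rank test replaces it. No period or sequence term appears anywhere. This is a named method, not a detail left open for a separate analysis plan.

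Sample size is 15-20 in the Project summary. The Participants section has a wider range: "In this study, 15-25 trained bodybuilders were recruited".

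Two other places bear on whether the visits might differ. In the Experimental procedure, "participants were free to adjust the resistance and speed of the bike according to their own feelings" and "they were free to arrange the rest time". The only session described before the first ride is the Pre test, in which athletes were "tested at different speeds of 1, 2, 3, 4, and 5 miles per hour on a 0-degree incline for 3 minutes each".

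**The concern.** In a two-period crossover, each athlete's caffeine-minus-placebo difference mixes the treatment effect with whatever changed between the visits. That change has one sign in athletes who take caffeine first and the opposite sign in those who take placebo first. A paired test treats all the differences as one sample. It therefore counts the systematic gap between the two orders as random noise and, if one order is larger, lets part of that gap into the estimate.

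A visit effect is plausible here. Pace and rest are self-chosen, and the Pre test is a short graded test, not a practice of the dehydration ride. The first ride under this procedure is therefore already a scored visit. With 15 to 25 athletes there is little power to spare, and the order of visits is known for every athlete, so this noise can be removed.

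**Working it through.** The protocol states no power, effect size or SD, so there is no figure of its own to reproduce.

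**Inputs from the protocol.** Two visits, two treatments, N between 15 and 25, significance level 0.05.

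**Assumptions.** Two-sided testing, normal errors, no carryover. The visit effect k is the first-minus-second-visit change, in units of the within-order SD of the paired difference, taken as 0, 0.25, 0.5 and 1.0. The true effect τ is set to give the paired t-test 80% power at k = 0: 0.78, 0.66 and 0.58 SD at N = 15, 20 and 25.

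**Model.** The difference d (caffeine minus placebo) is τ + k + e when caffeine comes first (n1 athletes) and τ − k + e when placebo comes first (n2 athletes), with SD(e) = 1.

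- Paired t-test: shift = k(n1 − n2)/N. The SD of d becomes √(1 + k²·4·n1·n2/(N(N − 1))).
- Adjusted test: the estimate is the average of the two order-specific mean differences, with SE = (s/2)·√(1/n1 + 1/n2), where s is the pooled within-order SD, on N − 2 degrees of freedom. Here k cancels.

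**SD inflation at 10:10.** The factor 4·n1·n2/(N(N − 1)) is 400/380 = 1.053.

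- k = 0.25: √(1 + 0.0625 × 1.053) = 1.03
- k = 0.5: √(1 + 0.25 × 1.053) = 1.12
- k = 1.0: √(1 + 1.053) = 1.43

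**Power and type I error at 10:10, τ = 0.66** (simulation, 200,000 runs per cell):

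| k | Paired-t power | Adjusted power | Paired-t type I error | Interval width, paired ÷ adjusted |
|---|---|---|---|---|
| 0 | 0.799 | 0.796 | 0.050 | 0.997 |
| 0.25 | 0.781 | 0.797 | 0.044 | 1.03 |
| 0.5 | 0.723 | 0.798 | 0.030 | 1.12 |
| 1.0 | 0.495 | 0.798 | 0.006 | 1.43 |

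The adjusted test keeps a type I error of 0.050 to 0.051 throughout. At 10:10 the two tests have equal power at k of about 0.1.

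**Unequal orders at k = 0.5.** The two paired-t values are for a visit effect that helps or opposes the treatment effect.

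| Split | Shift in the estimate (SD) | Paired-t power | Adjusted power |
|---|---|---|---|
| 8:7 | 0.5 × 1/15 = 0.033 | 0.759 or 0.680 | 0.794 |
| 13:12 | 0.5 × 1/25 = 0.020 | 0.756 or 0.691 | 0.798 |
| 12:8 | 0.5 × 4/20 = 0.100 | 0.846 or 0.573 | 0.782 |

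**If order were assigned by simple randomisation (an assumption).** At N = 20, the chance of 12:8 or worse is 1 − (2 × 167,960 + 184,756)/1,048,576 = 0.50. Averaged over splits, paired-t type I error is 0.049 to 0.050, and power is 0.775, 0.707 and 0.502 at k = 0.25, 0.5 and 1.0. Conditional on a poor split, the paired test can exceed its level: type I error is 0.075 at 13:7 with k = 1.0.

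**Fallback tests at 10:10** (power, signed-rank against rank-sum on period differences; 20,000 to 30,000 runs per cell; heavy-tailed case at τ = 0.5 SD):

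| k | Normal errors | Heavy-tailed (t, 3 df) errors |
|---|---|---|
| 0 | 0.779 / 0.753 | 0.780 / 0.747 |
| 0.25 | 0.757 / 0.753 | 0.739 / 0.744 |
| 0.5 | 0.693 / 0.752 | 0.611 / 0.745 |
| 1.0 | 0.437 / 0.754 | 0.233 / 0.744 |

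At 8:7 with normal errors and k = 0, the pair is 0.779 / 0.735.

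**The case against.** The planned test is not wrong in the usual sense. With equal orders it is unbiased and conservative, and over randomisation it holds its level, so what is at stake is efficiency. That stands.

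The larger losses need a large visit effect. Against the assumed treatment effect of 0.66 SD at N = 20, k = 0.25 is 38% as large (0.25/0.66), k = 0.5 is 76% and k = 1.0 is 152%. At k = 0.25 the loss is under two points. The documents do not support any particular k, and several features argue for a small one: start time, hydration check, temperature, humidity and training are held constant, and the athletes have "participated in national bodybuilding competitions with adequate pre-competition dehydration experience". The pacing argument is also weaker for urine specific gravity than for energy expenditure or dehydration rate, because both visits begin from a hydration check and end at the same relative weight loss. All of this stands, and it limits how strongly the point can be pressed.

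The break-even near k = 0.1 applies to 10:10. Averaged over the two directions, it is about 0.14 at 8:7 and a little above 0.2 at 12:8. The shift is negligible at 8:7 or 13:12, and silence on allocation does not show that orders will be unequal. The rank-sum fallback also has a real cost if there is no visit effect.

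None of this removes the reason for the change. The adjustment costs a fraction of a point in near-balanced orders when it is not needed, and saves about 7 or 8 points at k = 0.5 and 30 at k = 1.0 (10:10) when it is.

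**Conclusion.** The concern holds, as a point that should be acted on but does not invalidate the trial. The protocol commits a two-visit crossover to tests that cannot remove a visit effect. At N = 20 and 10:10, the confidence interval is 3%, 12% or 43% wider than it need be at k = 0.25, 0.5 or 1.0, and power falls from 0.80 to 0.78, 0.72 or 0.49. The shift matters only if the orders are materially unequal: 0.2 times the visit effect at 12:8, against 0.07 at 8:7 and 0.04 at 13:12.

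The mechanism is algebra and is certain. The size rests on assumed visit effects, an assumed treatment effect, two-sided testing and normal errors. With no visit effect, the planned test is valid and marginally more powerful than the adjusted one.

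**What to change.** Replace the paired t-test with a period-adjusted crossover analysis: a linear mixed model with treatment, period, sequence and a random participant effect. With complete data this is equivalent to a two-sample t-test comparing within-person period differences between the two orders. For the non-normal case, replace the signed-rank test with the rank-sum test on the same period differences. State that order is allocated in balanced blocks: adjustment removes the shift, but power still depends on balance (0.78 at 12:8 against 0.80 at 10:10).

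The cost is two sentences in the statistical section, one degree of freedom and no new data. If there is no visit effect, the adjusted t-test gives up 0.2 points of power at 10:10 or 13:12, 0.6 at 8:7 and 1.9 at 12:8. The rank-sum fallback gives up more: 2.6 points at 10:10 and 4.4 at 8:7 under normal errors. At 10:10 it is about level with the signed-rank test at k = 0.25, and at k = 0.5 it gains 6 points (13 with heavy-tailed errors). The case for the fallback is therefore weaker than for the main analysis.

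The adjustment does not address carryover between visits.
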